#### SDMT Z-score Calculation

For the SDMT, the z-score for each patient at each time-point will be created by subtracting the reference population's baseline mean score on the SDMT from the patient's SDMT score and dividing by the baseline SD on the SDMT of the reference population, i.e.

$$Z_{SDMT} = \frac{SDMT \text{ raw score} - MEAN(reference)}{SD(reference)}$$

and SDMT raw score = # of correct items within the timeframe of the test. The reference population will be the study population.

For missing post-Baseline values, if a patient is missing the SDMT score due to MS related physical limitation or other physical limitations, then a score of 0 will be assigned. If the reasons for missing score is due to other reasons (non-compliance, missed visits), then LOCF from post-Baseline values will also be used as to impute the z-score for that visit. If a value is not available to carry forward, the mean of the available z-scores using all available data from the same treatment group, will be calculated at the specified visit and used as the imputed value. Values imputed using the mean will not be carried forward to other visits.

The change from Baseline in the MSFC scores and the actual values at each visit will be summarized in each treatment group. The changes in MSFC scores at Month 24 will be analyzed and compared between treatment groups using an ANCOVA model adjusting for region, EDSS category at Baseline, and the Baseline MSFC score.

LCLA is performed with standardized set of charts (Sloan charts or Tumbling E charts) to assess low contrast visual acuity. Each chart corresponds to a different contrast level, and charts are scored according to the number of letters that are identified correctly.

Change from Baseline in visual function test scores as assessed by LCLA will be summarized by treatment group and time point, and will be compared at Month 24 between treatment groups using ANCOVA adjusted for region, EDSS category at Baseline, and the Baseline visual function test score.

### Secondary Endpoint: Change in MSQOL-54 score from Baseline to Month 24

Actual scores and change from Baseline by visit will be summarized for each of the 12 subscales, the 2 summary scores, and the 2 single-item measures shown below:

- Subscales
  - 1. Physical function
  - 2. Role limitations physical
  - 3. Role limitations emotional
  - 4 Pain
  - 5. Emotional well-being
  - 6. Energy
  - 7. Health perceptions
  - 8. Social function
  - 9. Cognitive function
  - 10. Health distress
  - 11. Overall quality of life
  - 12. Sexual function
- Summary scores
  - 1. Physical health composite summary
  - 2. Mental health composite summary
- Single item measures
  - 1. Satisfaction with sexual function
  - 2. Change in health

Comparisons of the change from Baseline to Month 24 for the 2 summary scores only between treatment groups will be analyzed by an ANCOVA model adjusted for region, EDSS category at Baseline, and Baseline summary score of interest. Missing data will be imputed using a mixed-effects regression model (random slope and intercept).

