#### Part B

Approximately 1200 patients with RMS will be randomized in this part of the study (approximately 400 per treatment group). The primary analyses will compare the ARRs in each of the RPC1063 groups to the IFN  $\beta$ -1a group using a Poisson regression model at the alpha = 0.025 level. The control ARR is assumed to be equal to 0.3 (Mikol, 2008). Assuming extra-Poisson variation ( $\sigma^2$ =1.3) (Polman, 2011) and 24 months of follow-up per patient, a total sample size of 999 patients (333 per arm) is estimated to provide 90% power to detect a 37% reduction in the ARR (i.e., an ARR of 0.19 for RPC1063) (Nicholas, 2011). In order to account for an assumed dropout rate of 17%, approximately 1200 patients (400 per arm) will be enrolled.

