### 5. GENERAL STATISTICAL CONSIDERATIONS

Statistical testing for the primary efficacy endpoint will be made between each RPC1063 group and the IFN  $\beta$ -1a group (2 treatment contrasts). To account for multiple comparisons, each of the 2 treatment comparisons will be tested at the alpha = 0.025 level.

To control for type 1 error, the 3 key secondary endpoints will be tested in order in a sequential, that ranks the RPC1063 1 mg dose above the RPC1063 0.5 mg dose and the key secondary endpoints in the order shown in section 4.2. If both doses are significant on the primary endpoint, then the first comparison on the key secondary endpoints will be between the RPC1063 1 mg group and the IFN  $\beta$ -1a group at the 5% level of significance. If that comparison is successful, then the same endpoint will be tested for the RPC1063 0.5 mg group vs. the IFN  $\beta$ -1a group comparison at the 5% level of significance. This procedure (Figure 2A) will continue down the rank ordered key secondary endpoint list until a comparison fails to reach statistical significance,

For the 3rd key secondary endpoint of time to onset of sustained disability progression, the data from this study will also be pooled with the data from another phase 3 study, RPC01-301, for hypothesis testing. This pooling will be described in a separate pooling plan.

If only 1 RPC1063 dose is significant on the primary endpoint, then on the rank ordered key secondary endpoint list for the surviving dose only, at the 2.5% level of significance for each key secondary endpoint (Figure 2B).

Figure 2.

Other secondary endpoint analyses will not include adjustments made for multiple comparisons and multiple endpoints.

Unless specified otherwise, all statistical analyses will be performed using a two-sided hypothesis test at the overall 5% level of significance. All p-values will be rounded to four decimal places. If a p-value is less than 0.0001, it will be reported as "<0.0001". If a p-value is greater than 0.9999, it will be reported as ">0.9999".

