### 5.1. Sample Size

Approximately 1200 patients with RMS will be randomized in this study (approximately 400 per treatment group). The primary analyses will compare the ARRs in each of the RPC1063 groups to the IFN  $\beta$ -1a group using a Poisson regression model at the alpha = 0.025 level. The control ARR is assumed to be equal to 0.3 (Mikol, 2008). Assuming extra-Poisson variation ( $\sigma^2$ =1.3) (Polman, 2011) and at least 12 months of follow-up per patient, the method of Nicholas (Nicholas, 2011) results in a total sample size of 1059 patients (353 per arm) in order to provide 80% power to detect a 43% reduction in the ARR (i.e., an ARR of 0.17 for RPC1063). To account for an assumed dropout rate of approximately 12%, approximately 1200 patients (400 per treatment group) will be enrolled.

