## 9.3. Other Secondary Efficacy Endpoints

The other secondary endpoints are:

- Proportion of patients who are GdE lesion-free at Month 24
- Proportion of patients who are new or enlarging T2 lesion-free at Month 24
- Percent change in normalized brain volume (atrophy) on MRI scans from Baseline to Month 24
- Change in MSFC score from Baseline to Month 24 (including the low-contrast letter acuity test [LCLA] measurement of visual function as a component)
- Change in MSQOL-54 score from Baseline to Month 24

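### The MSQOL-54 imputation rule reads as a single mixed-model fill followed by ordinary ANCOVA; on that reading it either overstates precision or dilutes the effect, depending on an unstated model term

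*SAP*

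**What the plan says.** SAP Section 9.3 lists "Change in MSQOL-54 score from Baseline to Month 24" among the other secondary endpoints. Under Section 9.3.1 only the two summary scores are tested. Their change to Month 24 "will be analyzed by an ANCOVA model adjusted for region, EDSS category at Baseline, and Baseline summary score of interest". The next sentence is the whole missing-data rule: "Missing data will be imputed using a mixed-effects regression model (random slope and intercept". No sensitivity analysis is given for this endpoint.

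On error rates, SAP Section 5 sets the general rule that, unless specified otherwise, "all statistical analyses will be performed using a two-sided hypothesis test at the overall 5% level of significance", and adds: "Other secondary endpoint analyses will not include adjustments made for multiple comparisons and multiple endpoints".

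Protocol Table 3 schedules MSQOL-54 at Baseline and Months 6, 12, 18 and 24. Protocol Table 4 and Section 10.5 also collect it at the Early Termination visit. The follow-up visit 4 weeks after the last dose (Section 10.6) does not.

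**The concern.** A value predicted from a mixed model has less spread than the score it replaces, and the prediction is itself estimated. An ANCOVA run once on the filled-in data counts each prediction as an observed score, so neither source of uncertainty reaches the standard error.

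The sentence does not say that the fill is single, but the context points that way. The SAP's other efficacy imputations are one-off fills: group mean and LOCF for T2 and GdE lesions, non-responder and LOCF for lesion-free status, LOCF for brain volume, and assigned values, LOCF or group mean for the MSFC components. Multiple imputation and a combining rule appear nowhere. A programmer following the text would most likely output predicted Month 24 scores and run one ANCOVA.

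Missing Month 24 scores are to be expected. The ITT population keeps every dosed patient, and for early discontinuers the visit schedule provides MSQOL-54 at the Early Termination visit but not at follow-up. At stake are the interval and p-value for each dose on the endpoint that serves the quality-of-life objective.

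**Working it through.** **The plan's own figures.** The documents give no SD, power or missing share for MSQOL-54. The arm size and dropout used below come from the relapse-rate sample size, so that was reproduced first, with n per arm = φ(z₁₋α/₂ + z_power)²(1/(λ₀t) + 1/(λ₁t)) / ln(λ₁/λ₀)², φ = 1.3 and α = 0.025 taken as two-sided.

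- SAP 5.1 (0.30 v 0.17, 12 months, 80% power): 1.3 × (2.241 + 0.842)² × (3.333 + 5.882) / 0.3226 = 353.0. This matches 353. With 12% dropout, 353/0.88 = 401.1, about 400.
- Protocol 13.2 (0.30 v 0.19, 24 months, 90% power): 332.4, which matches 333. With 17% dropout, 333/0.83 = 401.2, about 400.

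**Inputs from the documents.** 400 per arm in three arms; visits at 0, 6, 12, 18 and 24 months; ANCOVA on change with baseline score; two-sided 5%; missing share 12% (SAP: "To account for an assumed dropout rate of approximately 12%, approximately 1200 patients (400 per treatment group) will be enrolled") or 17% (Protocol: "In order to account for an assumed dropout rate of 17%, approximately 1200 patients (400 per arm) will be enrolled").

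**Assumptions not in the documents.** Score SD 20; between-patient share of variance 0.4 or 0.6; slope SD 4 per year; monotone dropout, missing completely at random (MCAR) plus one missing-at-random (MAR) run; variance components treated as known; a 30% row added to show the trend.

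**Simulation under no treatment effect, 8000 trials per row.** Each cell shows type 1 error, then mean model SE divided by the true SD of the estimate.

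| Missing | Between-patient share | Single prediction, treatment in model | One random draw, treatment in model | Single prediction, treatment omitted | Multiple imputation (20), treatment in model |
|---|---|---|---|---|---|
| 12% | 0.4 | 8.1%, 0.90 | 7.7%, 0.91 | 5.3%, 0.99 | 4.9%, 1.01 |
| 12% | 0.6 | 7.8%, 0.90 | 7.4%, 0.91 | 5.3%, 0.99 | 4.8%, 1.00 |
| 17% | 0.4 | 8.6%, 0.88 | 8.1%, 0.89 | 5.0%, 1.00 | 4.4%, 1.03 |
| 17% | 0.6 | 8.6%, 0.88 | 8.2%, 0.89 | 5.2%, 1.00 | 4.6%, 1.02 |
| 17% (MAR) | 0.6 | 8.6%, 0.88 | 8.1%, 0.89 | 5.0%, 1.00 | 4.5%, 1.02 |
| 30% | 0.6 | 12.8%, 0.77 | 11.2%, 0.81 | 5.8%, 0.99 | 5.3%, 1.02 |

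With no missing data, type 1 error was 4.8% to 5.5%. The 95% Monte Carlo error is about ±0.5 points (±0.7 at 12.8%).

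**Check on the link between the two figures.** If the SE is a fraction r of its true value, type 1 error is 2[1 − Φ(1.96r)]. At r = 0.90 this is 7.8%, and at r = 0.88 it is 8.5%, in line with the table. At r = 0.94 it is 6.5%.

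**Early Termination score.** A smaller simulation (1500 trials per scenario, Monte Carlo error about ±1.4 points) with this score used in the prediction gave about 7% to 8% at 12% missing and 9% at 17% with treatment in the model, and about 4% to 6% with treatment omitted. A score close to dropout makes the prediction better, so the range for the SE shortfall is taken as 6% to 12% rather than only the table's 10% to 12%.

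**Size of the dilution.** With treatment omitted, imputed scores are drawn towards a mean common to all arms. If a share m is imputed and those scores carry a fraction k of the true effect, the estimate is roughly (1 − m) + mk of that effect. At the extreme k = 0 the loss is m itself, 12% to 17%. Patients' own earlier scores carry part of the effect, which makes the loss smaller.

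**The case against.** A reader might infer that the SAP prescribes a single fill and that the MSQOL-54 p-values will therefore be too favourable. The documents do not support either step as fact.

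- **Single fill.** The number of imputations is not stated. The same sentence is compatible with multiple imputation, which held 4.4% to 5.3% in the table. This stands; a single fill is the natural reading, not the only one.
- **Treatment in the model.** Inflation also needs treatment in the imputation model, which is not stated either. Without it, type 1 error was 5.0% to 5.8% and the bias runs against the drug. This stands. It does not rescue a single fill, because the cost then falls on the estimate. The SAP's own mean imputations use the patient's treatment group, so a treatment-specific model is at least plausible.
- **Magnitude.** The variance components are assumed, and the 12% and 17% are allowances for the relapse-rate sample size, not forecasts of missing MSQOL-54 scores. The protocol also says that efforts will be made to follow patients who stop treatment for disease status. This stands; the figures are a range under assumptions.
- **Consequence.** Two doses by two scores are already four tests without multiplicity adjustment, outside the controlled sequence. This stands and limits the weight of the point.

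**Conclusion.** The rule is under-specified, and its most natural reading is a poor method. Under a single fill with treatment in the imputation model, standard errors are about 6% to 12% too small and type 1 error is about 7% to 9% instead of 5% at 12% to 17% missing. Under a single fill with treatment omitted, type 1 error stays near 5% and a real difference is understated. Neither outcome is certain from the text, since both depend on choices that the SAP leaves open.

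The figures rest on the assumed variance components and on the planned dropout rates standing in for the missing share. The effect is confined to an unadjusted other secondary endpoint. It is still worth correcting: the endpoint serves a stated objective, has no sensitivity analysis that would reveal the problem, and a better method needs little work.

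**What to change.** Keep the ANCOVA in SAP Section 9.3.1 and apply it to multiple imputations from the same random intercept and slope model. State that the imputation model includes treatment and treatment-by-time, that both parameters and residuals are drawn, how many imputations are made (20 were enough in the check), and that results are combined by Rubin's rules.

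An alternative is to take the Month 24 contrast and its standard error directly from a mixed model with those terms. That departs from the ANCOVA that protocol Section 13.6.4 names for continuous other secondary endpoints, so it would need to be declared. The same edit could reconcile the covariates: that protocol section adjusts for age, while the SAP uses EDSS category in its place.

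The cost is a paragraph of SAP text before database lock, a little more programming, and wider intervals than a single fill with treatment in the model. From the simulated SE/SD ratios and SDs at between-patient share 0.6, the SE rises from 0.903 × 1.331 = 1.202 to 1.003 × 1.333 = 1.337 at 12% missing (11% wider). At 17% it rises from 0.878 × 1.336 = 1.173 to 1.020 × 1.342 = 1.369 (17% wider). That is precision the single fill did not have.

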## 9.4. Exploratory Efficacy Endpoints

The exploratory endpoints are:

### 10. SAFETY ANALYSIS

All analysis of safety will be conducted using the Safety population. Statistical hypothesis testing will not be performed on any safety results. No imputation of missing safety data will be performed.

#### 10.1. Adverse Events

A treatment emergent AE is any reaction, side effect, or other untoward event, regardless of relationship to study drug, which occurs any time after the first dosing of study drug, until 28 days following the last dose of study drug. During the study, clinically significant adverse changes in clinical status, ECGs, and physical examinations are considered AEs. Any patient complaints associated with such an abnormal finding will also be reported as an AE.

Adverse events include, but are not limited to: (1) a worsening or change in nature, severity, or frequency of conditions present at the start of the study; (2) patient deterioration due to primary illness; (3) intercurrent illness; and (4) drug interaction.

An abnormal laboratory value will only be reported as an AE if it involves therapeutic medical intervention, if the Investigator considers it to be an AE, or if it leads to study discontinuation.

A treatment-emergent AE is defined as an AE that meets any of the following conditions:

- Begins on or after Study Day 1
- Begins before Study Day 1 and worsens in severity on or after Study Day 1.

Adverse events with unknown onset dates or unknown end dates will be counted as having occurred during the study treatment period unless the event resolves before Study Day 1. Adverse events with unknown severity will be counted as severe. Adverse events with unknown relationship to study drug will be counted as probably related to study drug.

Only treatment-emergent AEs will be presented, according to the Medical Dictionary for Regulatory Activities (MedDRA®), system organ class (SOC), and preferred term (PT).

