## 12.1. Adverse Events (AEs)

The AE definitions and reporting procedures provided in this protocol comply with current CFR 21 Part 312. An AE is any untoward medical occurrence that does not necessarily have a causal relationship with the investigational medicinal product. An AE can therefore be any unfavorable or unintended sign, including an abnormal laboratory finding, symptom or disease temporally associated with the use of an investigational medicinal product whether or not considered related to the investigational medicinal product.

Relapses and MS disease progression will be monitored as study endpoints, but will not be recorded as AEs.

AEs will be monitored throughout the entire study. Investigators will ask the patient at each visit if they have experienced any untoward occurrence since the last study visit. All AEs will be recorded on the eCRFs provided: a description of the event, severity, time of occurrence, duration, any action (e.g. treatment and follow up tests) and the outcome should be provided along with the Investigator's assessment of the relationship to the study treatment.

AEs will be recorded from the start of study drug treatment until 28 days following the last dose of treatment with the study drug.

If known, the event diagnosis should be recorded rather than listing individual signs or symptoms. AEs must be graded as being mild, moderate or severe and their approximate duration given. Definitions of severity are as follows:

Mild: an AE usually transient in nature and generally not interfering with normal activities;

Moderate: an AE that is sufficiently discomforting to interfere with normal activities;

Severe: an AE that is incapacitating and prevents normal activities.

Even if the Investigator feels there is no relationship to the study drug, all AEs MUST be recorded in the eCRF. The Investigator is requested to assess the relationship of any AEs to treatment using the following definitions:

Unrelated: those AEs which are clearly and incontrovertibly due to extraneous causes (concurrent drugs, environment etc.) and do not meet the criteria for drug relationship listed under Unlikely, Possible, Probable or Related.

Unlikely: an AE may be considered unlikely if it includes at least the first two features:

• It does not follow a reasonable temporal sequence from administration of the drug.

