# **12.2.** Serious Adverse Events (SAEs)

An SAE is any untoward medical occurrence or effect that fulfills the following criteria:

- Results in death
- Is life-threatening (NOTE: the term "life-threatening" refers to an event in which the patient was at risk of death at the time of the event; it does not refer to an event which hypothetically might have caused death if it were more severe)
  - o Requires hospitalization or prolongation of existing inpatient hospitalization

01 October 2014 Version 4.0

- Results in persistent or significant disability or incapacity
- Is a congenital abnormality/birth defect
- Important medical events not captured by the above but which may, for example, require medical intervention to prevent one of the outcomes above.

Medical and scientific judgment should be exercised in deciding whether expedited reporting is appropriate in other situations, such as important medical events that may not be immediately life-threatening or result in death or hospitalization but may jeopardize the patient or may require intervention to prevent one of the other outcomes listed in the definition above. These should also usually be considered serious. Examples of such events are intensive treatment in an emergency room or at home for allergic bronchospasm; blood dyscrasias or convulsions that do not result in hospitalization; or development of drug dependency or drug abuse.

Uncomplicated cases of relapse and MS disease progression requiring hospitalization or otherwise meeting the above serious criteria do not need to be reported as SAEs, unless there are other diagnoses or complications which meet serious criteria.

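### SAP 10.1 counts deterioration of the primary illness as an adverse event with no exception for MS relapse or progression, contradicting Protocol 12.1 and 12.2; it also gives two treatment-emergent windows

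*SAP*

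**What the plan says.** **What counts as an AE.** SAP 10.1 gives a numbered list of things that are adverse events. Item (1) is "a worsening or change in nature, severity, or frequency of conditions present at the start of the study"; item (2) is "patient deterioration due to primary illness". Neither item excepts multiple sclerosis.

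Protocol 12.1 says the opposite for the trial's own endpoints: "Relapses and MS disease progression will be monitored as study endpoints, but will not be recorded as AEs". Protocol 12.2 extends this to serious events: "Uncomplicated cases of relapse and MS disease progression requiring hospitalization or otherwise meeting the above serious criteria do not need to be reported as SAEs". The exemption falls away where a further diagnosis or complication qualifies in its own right. SAP 10.1.4, which defines SAEs, does not repeat that exception.

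The protocol is not wholly consistent on this. Section 9.1.2.2, in setting out the treating investigator's duties, names suspected neurological worsening and relapse among the AEs to be assessed, with causality, and treated.

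**Treatment-emergent window.** SAP 10.1 defines the term twice. The opening sentence runs from first dosing "until 28 days following the last dose of study drug", which agrees with AE recording in Protocol 12.1. A later bulleted definition admits any event that "Begins on or after Study Day 1", with no end date, or that began earlier and then worsened. Protocol 12.3 collects SAEs through the last visit as well as within 28 days of last dose.

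**SAE criteria.** Protocol 12.2 includes "Is a congenital abnormality/birth defect", and Protocol 12.9 repeats the rule. SAP 10.1.4 omits it.

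**The concern.** Relapse is the primary endpoint, and the trial is planned on the expectation that there will be more relapses on IFN β-1a than on RPC1063. A relapse recorded as an AE would be tabulated under SAP 10.1, because nothing in the SAP takes it out. If RPC1063 is effective, such records would fall more often in the interferon arm, and the AE and SAE tables would show part of the efficacy result a second time, as a safety difference.

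The ambiguous cases are easy to foresee. SAP 9.1.2 plans a sensitivity analysis that adds unconfirmed relapses, so episodes that look like relapses but are not confirmed are expected. Protocol 12.1 does not say whether its exclusion covers them, and items (1) and (2) of the SAP list would take them in. SAP 10.1 also counts events with unknown severity as severe and events with unknown relationship as probably related, so an incomplete record would be tabulated at a high grade.

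The two treatment-emergent definitions are a separate fault: an SAE with onset after day 28 off drug is counted under one and not under the other.

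**Working it through.** **1. Inputs.** Protocol 13.2: control ARR 0.30, RPC1063 ARR 0.19, 24 months, σ² = 1.3, α = 0.025 per comparison, 90% power, 333 per arm. SAP 5.1: ARR 0.30 against 0.17, at least 12 months, 80% power, 353 per arm. Both plan about 400 randomized per arm.

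**2. Check that the planning rates are read as the plan uses them.** With n per arm = σ²·(1/(λ₀t) + 1/(λ₁t))·(z₀.₉₈₇₅ + z_power)² / [ln(λ₁/λ₀)]²:
- Protocol: 1.3 × (1/0.60 + 1/0.38) × (2.241 + 1.282)² / (ln 0.6333)² = 332.4, rounded up to 333, as stated.
- SAP: 1.3 × (1/0.30 + 1/0.17) × (2.241 + 0.842)² / (ln 0.5667)² = 352.98, rounded up to 353, as stated.

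**3. Upper bound: every relapse recorded as an AE, full 24 months.** The mean per patient is μ = ARR × 2. Relapses per 400 patients = 400μ. The proportion with at least one is 1 − exp(−μ) under Poisson, or 1 − 1.3^(−μ/0.3) for a negative binomial with variance 1.3 × mean.

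| Arm | μ | Relapses per 400 | ≥1, Poisson | ≥1, variance 1.3 × mean |
|---|---|---|---|---|
| IFN β-1a, 0.30 | 0.60 | 240 | 45.1% | 40.8% |
| RPC1063, 0.19 | 0.38 | 152 | 31.6% | 28.3% |
| RPC1063, 0.17 | 0.34 | 136 | 28.8% | 25.7% |

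At 0.19 the gap is 45.1 − 31.6 = 13.5 points (Poisson) or 40.8 − 28.3 = 12.5 points. The excess in the interferon arm is 240 − 152 = 88 events per 400, or 240 − 136 = 104 at the SAP's rate.

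**4. Partial recording.** The documents give no recording rate, so the share f is an assumption. Expected events per 400 over 24 months are 400 × μ × f.

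| Share recorded | IFN β-1a | RPC1063 (0.19) | RPC1063 (0.17) |
|---|---|---|---|
| 0 (protocol followed) | 0 | 0 | 0 |
| 5% | 12 | 7.6 | 6.8 |
| 10% | 24 | 15.2 | 13.6 |
| 100% | 240 | 152 | 136 |

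**5. Effect on overall TEAE incidence at the upper bound.** Assume a background incidence b that is equal in both arms and independent of relapse; the documents give no value. Incidence is then 1 − (1 − b)·exp(−μ), using 0.30 against 0.19.
- b = 60%: 1 − 0.4 × 0.5488 = 78.0% against 1 − 0.4 × 0.6839 = 72.6%, a difference of 5.4 points.
- b = 80%: 1 − 0.2 × 0.5488 = 89.0% against 1 − 0.2 × 0.6839 = 86.3%, a difference of 2.7 points.

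**6. Treatment-emergent window.** AE recording stops at 28 days under Protocol 12.1, so non-serious AEs are barely affected. After stopping drug, the scheduled visits are the Early Termination visit and one follow-up at 4 weeks (Protocol 9.4.4.1, 10.6, Table 4). Protocol 9.1 states an intention to follow patients who discontinue, even on other therapy, but sets no later visits. The two definitions therefore differ mainly on SAEs reported after day 28, which are likely to be few.

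**The case against.** The strongest reply is that the route is closed upstream. The SAP tabulates what sites record, sites work to the protocol, and Protocol 12.1 tells them not to record relapse or progression as AEs. SAP Section 2 says the plan is to be read together with the protocol, and no SAP step turns relapse or EDSS data into AE records. This stands, and it is why the lower bound is exactly zero. It does not remove the conflict: Protocol 9.1.2.2 itself speaks of relapse among AEs, and the SAP has no rule for discarding such a record if one arrives.

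Safety is descriptive, without hypothesis tests, and AEs are tabulated by preferred term and listed, so a misplaced relapse could be seen under its own term. That also stands, although the overall incidence rows could still shift.

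Not all deterioration of MS is a relapse or progression as Protocol 9.1.2.3 and 9.1.2.4 define them. Worsening of spasticity, pain or fatigue below those thresholds may properly be an AE. Item (2) therefore has a legitimate use, and deleting it outright would go too far.

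Three stronger readings are tempting and not supported. A reader might infer that relapses will enter the safety tables; the documents show only that they could. A reader might take the 13-point gap as an expected bias; it requires every relapse to be recorded against Protocol 12.1. And a reader might think the open-ended window or the missing birth-defect criterion lets efficacy failures in; neither does. Birth defects are already reportable as SAEs under Protocol 12.2 and 12.9, and nothing in the SAP drops a reported SAE.

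**Conclusion.** The contradiction on AE scope is certain from the text. Its effect is uncertain: zero if sites follow Protocol 12.1, and at most 45% against 32% of patients with a relapse tabulated as an AE (41% against 28% with variance 1.3 × mean), at ARR 0.30 against 0.19 over a full 24 months. The corresponding excess is 0 to 88 interferon events per 400, or up to 104 at the SAP's rate of 0.17. The direction follows from the planning rates and holds only if RPC1063 reduces relapses and some relapses are recorded as AEs; the documents do not state it.

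The two treatment-emergent definitions are an inconsistency within SAP 10.1, since one of them agrees with the protocol; few events are likely to be affected. The birth-defect omission is a minor alignment point with essentially no effect on reporting. Taken together, the wording should be corrected before database lock; no confirmatory efficacy analysis is touched.

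**What to change.** In SAP 10.1:
- State that protocol-defined MS relapse and disease progression are excluded from the AE and SAE tables unless another diagnosis or complication qualifies, citing Protocol 12.1 and 12.2. Apply this to both item (1) and item (2), and keep item (2) for MS worsening that meets neither definition.
- Say how unconfirmed relapses are handled if they appear on the AE form.
- Keep one treatment-emergent definition: onset or worsening from first dose to 28 days after last dose. List later SAEs separately.

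In SAP 10.1.4, add congenital abnormality or birth defect to match Protocol 12.2.

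If the protocol is amended for other reasons, the wording in 9.1.2.2 should be reconciled with 12.1.

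The cost is SAP text and one filter in the safety programming. Alpha, power, sample size and data collection are unchanged.
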